A docu-drama group of purposively selected 10 first-time donors will be formed. They will attend one meeting to watch two docu-dramas, each lasting 15 minutes, followed by a one-hour focus group discussion on the content of the drama, and feasibility, acceptability and cultural appropriateness of the intervention. Prior to, and after the viewing and discussion, a pre-, and post-test survey on the theory of planned behaviour constructs and implementation research measures will be conducted. Two study team members will facilitate the discussions. The docu-drama test-run will include an attendance list at the scheduled meeting. Those who attended, watch the 2 episodes, and stayed for the discussion will be considered as having adhered to the intervention.

The PROCEED Component will be addressed during the four years of the UH3 phase.

The PROCEED component involves exposing the interventions to participants and evaluating their outcomes. The UG3 pilot RCT will address the feasibility and inform the design of the PROCEED component.

The Theory of Planned Behaviour

As shown in Figure 4, according to the theory of planned behaviour, behavioural intention to return to donate in 6 months is influenced by factors such as attitude, subject norms, and perceived behavioural control, and has been examined in first-time blood donors (Masser et al., 2012). The theory of planned behaviour model will be used to evaluate the effect of intervention-specific changes in attitude, subject norms, and perceived behavioural control on intention to return to donate blood, and on actual return donation attempt.

[figure not shown]

Figure 3: Theory of planned behaviour

The Technology Acceptance Model

As shown in Figure 5, according to the technology acceptance model, intention to use technology (in this case, WhatsApp) is influenced by perceived usefulness and perceived ease of use of the technology (Venkatesh & Bala, 2008).

[figure not shown]

Figure 4: Technology Acceptance Model

Randomization

The docu-drama design and test-run will not employ randomization. The participants enrolled in the pilot RCT will be randomized immediately following the baseline assessment with a 1:1 allocation ratio to WhatsApp or control using blocked randomization (with randomly mixed

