A major assumption is that there will be high fidelity of the interventions. We will assess adherence to the interventions as a key element of fidelity (Carroll et al., 2007). Adherence will include subcategories of content, frequency, duration and dose (Carroll et al., 2007). The extent to which the intended content or frequency of WhatsApp and docu-drama are implemented will

represent the degree of implementation fidelity achieved for the two interventions (Carroll et al., 2007; Song et al., 2010).

Study Population

Inclusion Criteria

Docu-drama design

Design workshop participants will be drawn from blood donors, non-blood donors, drama experts, drama actors, and communication professionals. All must be at least 18 years old, consent to participate and understand English.

WhatsApp intervention design

Key informants will be drawn from the NBSG staff, community-based blood donation volunteers, blood donors, and non-blood donors. All must be at least 18 years old, consent to participate, and understand one of English, Twi, or Ga.

Pilot RCT

- At least 18 years-old
- First-time whole blood donor with the SZBC of the NBSG
- Eligible to donate again
- Consent to participate
- Understands one of English, Twi, or Ga
- Have a smart phone
- Have, or be willing to sign up for an active WhatsApp account

Docu-drama test-run

- At least 18 years-old
- First-time whole blood donor with the SZBC of the NBSG
- Eligible to donate again
- Consent to participate
- Understands one of English, Twi, or Ga

Exclusion Criteria

Docu-drama design

Do not meet the above inclusion criteria

WhatsApp intervention design

Do not meet the above inclusion criteria

Pilot RCT

History of more than one lifetime whole blood donation (with any blood centre)

Docu-drama test-run

History of more than one lifetime whole blood donation (with any blood centre)

Outcome measures

Primary Outcome

The primary outcome for the pilot RCT is to estimate the proportion of return blood donation attempts within six months of enrollment for each arm.

Secondary Outcomes

The secondary outcomes are the following measures.

WhatsApp and control

- Blood donation attitudes,
- subjective norms,
- perceived behavioural control,
- intention,
- ease of use of WhatsApp,
- perceived usefulness of WhatsApp.

Docu-drama, WhatsApp and control

- Intention of using the intervention

- Acceptability of the intervention
- Feasibility of the intervention
- Cultural appropriateness of the intervention

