The participants will be invited to participate in screening after blood donation at SZBC sites.

Table 1: Schedule of assessments for pilot RCT

Assessment	Screening (At first-time donation)	Baseline A pre- randomization (Day 0)	Baseline B post- randomization (Day 0)	6-month follow-up (Days 176- 190) ¹	6-12 months follow-up
Informed Consent Form	X				
Demographics	X				
Blood donation attitudes, subjective norms, perceived behavioural control, and intention		X		X	
Randomization			X		
Intention of using the intervention			X		
Acceptability of the intervention			X	X	
Feasibility of the intervention			X	X	
Cultural appropriateness of the intervention			X	X	
Perceived usefulness of the intervention			X	X	
Perceived ease of use of the intervention			X	X	
Intervention relatedness			X	X	
Return blood donation attempts ²				X	
Focus groups of participant views of acceptability, effectiveness, feasibility, and cultural appropriateness					X
Note: The participants involved in the test-run of the docu-drama will be surveyed prior-to and after the docu-drama with all instruments (except blood donation attempts) and participate in facilitator-led focus groups.					
¹ 6-months with a 2-week window.					
² Donor return will be assessed via telephone calls and cross-checked with SZBC donor records.					

Follow-up assessments for the pilot RCT

There will be two follow-up assessments.

6 months

The 6-month assessment for the pilot RCT will occur over the phone with a 2-week window of the 6-month pilot. Donor return will be assessed via telephone calls and cross-checked with SZBC donor records. The six-month follow-up will repeat baseline post-randomization questionnaires and include the intention of using the intervention, acceptability of the intervention, feasibility of the intervention, cultural appropriateness of the intervention, perceived ease of use of the intervention, perceived usefulness of the intervention, and intervention relatedness. In line with definitions of acceptability, appropriateness and feasibility given by Weiner et al. (2017), we defined these characteristics as follows:

Acceptability is the perception among first-time blood donors that an intervention is agreeable or satisfactory for promoting blood donation. Thus, acceptability will be measured with a five-item questionnaire.

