Cultural appropriateness is the perceived fit, relevance, or compatibility of an intervention; and/or perceived fit of these interventions for promoting blood donation among first-time blood donors (Weiner et al., 2017). Cultural appropriateness will be measured with a five-item questionnaire.

Feasibility is defined as the extent to which an intervention, can be successfully used by the NBSG to promote blood donation among first-time blood donors. Feasibility will be measured with a six-item questionnaire by integrating appropriateness measures (Weiner et al., 2017) and the role of culture as it pertains to health communication (Kreuter & McClure, 2004).

The extent to which respondents participated in the activities will also be documented for the WhatsApp intervention and includes not leaving the WhatsApp group during the intervention; evidence of having read a post, an indicator that can be used in closed WhatsApp groups such as the one to be implemented in the study, and posting at least once a month. Those not reading 50% of the weekly post by the moderator and not posting at least three times during the intervention will be considered as non-adherent. The WhatsApp group moderator will obtain participation data by checking the read status and post by participants.

6–12 months

The second follow-up will involve facilitator-led participant focus group (8 participants per group) discussions of views on acceptability, effectiveness, feasibility, and cultural appropriateness.

The participants involved in the test-run of the docu-drama will be surveyed after the docu-drama with all follow-up instruments (except blood donation attempts) and participate in facilitator-led focus-groups similar to participants in the pilot RCT.

All the constructs will be constructed using a 5-point Likert scale ranging from “completely disagree” to “completely agree”. Focus group discussions will also be held with 6–8 participants from each group to assess all the above implementation research outcomes of interventions.

Risk/Benefit Assessment

Known Potential Risks

Potential risks may include breach of confidentiality and any discomfort that may result from discussions of the docu-drama or issues about blood donation. However, these risks are minimal and are not more than those encountered in everyday life.

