5. I find myself actively involved in WhatsApp friends' lives	1 	2 	3 	4 	5 
6. I see WhatsApp friends as friendly and approachable	1 	2 	3 	4 	5 
7. I feel like an outsider when I'm on WhatsApp	1 	2 	3 	4 	5 
8. I see myself as a loner when I am on WhatsApp	1 	2 	3 	4 	5 
9. Even around WhatsApp friends I know, I don't feel that I really belong	1 	2 	3 	4 	5 
10. I feel disconnected from the WhatsApp world around me	1 	2 	3 	4 	5 
11. I don't feel related to most people on WhatsApp	1 	2 	3 	4 	5 
12. I don't feel I participate with anyone or any group on WhatsApp	1 	2 	3 	4 	5 

Signature: _____

Date: _____

8. Case Report Form for participants attending docu-drama prior to viewing

Baseline Docu-drama

Participant ID:

Form Date:
(example: 01-APR-2021)

--202
Day Month Year

Participant
3-letter code:

Bloodsafe Logo
Placeholder

01 Korle-Bu Bld Bank
02 Korle-Bu Maternity
03 Pentecost Hospital
04 LEKMA Hospital
05 Maamobi Polyclinic
06 Accra Shopping Mall
07 Mobile Unit

Complete this form for all participants attending the C-CAD docu-drama prior to viewing the docu-drama.

A. Intention of Using the Intervention

Yes No I don't know

1. I would participate in a docu-drama viewing and discussion on blood donation in the next 6 months 0 2
2. I would participate in a docu-drama viewing and discussion on blood donation as often as possible 0 2
3. I expect to participate in a docu-drama viewing and discussion on blood donation in the future 0 2

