- 2 No opportunity to donate (e.g. blood donation team did not return, or participant donated at a sponsored event that has not been held again)
- 3 Busy
- 4 No motivation to donate
- 5 Participant initially donated for sick individual (e.g. friend or family member) who no longer needs blood
- 6 Medical condition
- 7 No reminder
- 8 Participant not aware of when to return or where to donate
- 9 Distance to the donation site
- 10 Other, specify: _____

1 Yes →

1.b. Were any of the donation attempts successful (blood was donated)?

0 No → 1.c Indicate reason donation attempt was unsuccessful (use first attempt if more than 1)

- 1 Failed donation screening or failed donor selection
- 2 Unsuccessful venipuncture
- 3 Waiting time to donate was too long
- 4 Other, specify: _____

1 Yes →

1.d Who did the participant donate blood for?

- 1 A friend/acquaintance/colleague
- 2 A relative
- 3 The blood bank/Blood Service
- 4 The community
- 5 Other; specify: _____
- 6 No one in particular

Signature: _____

Date: _____

11. Case Report Form for participants attending docu-drama after viewing

Post Docu-drama

Participant ID:

Form Date:

(example: 01-APR-2021)

		 2	 0	 2
Day	Month	Year		

Participant
3-letter code:

Bloodsafe Logo
Placeholder

Site:

01 Korle-Bu Bld Bank
02 Korle-Bu Maternity
03 Pentecost Hospital
04 LEKMA Hospital
05 Maamobi Polyclinic
06 Accra Shopping Mall
07 Mobile Unit

Complete this form for all participants attending the C-CAD docu-drama after viewing the docu-drama.

A. Blood Donation Attitudes

Below are a number of statements relating to the participant's current attitude toward blood donation. Read each statement to the participant, and have them indicate where they fall on the scale from 1 to 5.

For the participant, donating blood within the next 4 months would be:

- | | | | | | | |
|--------------------------|----------------------------|----------------------------|----------------------------|----------------------------|----------------------------|-----------------------|
| 1. Useless |  1 |  2 |  3 |  4 |  5 | Useful |
| 2. Pointless |  1 |  2 |  3 |  4 |  5 | Worthwhile |

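### The docu-drama forms yield no before-and-after pair for the planned-behaviour constructs or for intention of use, although the protocol promises one

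*Combined protocol and SAP*

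**What the plan says.** Three places describe the survey of the 10 test-run participants.

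- Study Design, Docu-drama test-run: before and after the viewing and discussion, "a pre-, and post-test survey on the theory of planned behaviour constructs and implementation research measures will be conducted".
- Note to Table 1: these participants are "surveyed prior-to and after the docu-drama with all instruments (except blood donation attempts".
- Follow-up assessments, 6–12 months: they are "surveyed after the docu-drama with all follow-up instruments (except blood donation attempts".

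Two forms in Study Tools serve this group. Tool 8 carries the instruction "Complete this form for all participants attending the C-CAD docu-drama prior to viewing the docu-drama". Tool 11 carries the instruction "Complete this form for all participants attending the C-CAD docu-drama after viewing the docu-drama".

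Under Outcome measures, Secondary Outcomes, the list shared by docu-drama, WhatsApp and control begins with "Intention of using the intervention". For the randomized pilot, the text on the 6-month assessment says "The six-month follow-up will repeat baseline post-randomization questionnaires and include the intention of using the intervention", and the Month 6 form has that measure as section H. The Table 1 row for the same measure is marked at Baseline B only.

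**The concern.** A before-and-after comparison needs the same items at both times. The text promises this for the planned-behaviour constructs and the implementation measures, but each docu-drama form lacks a block that the other has.

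The docu-drama is left out of the pilot RCT and is being prepared for the UH3 trial, so the test-run is its only planned before-and-after survey in this phase. A missed pre-viewing answer cannot be recovered once the participant has watched the episodes. A missed post-viewing answer leaves a listed secondary outcome for the docu-drama without a value after exposure.

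**Working it through.** The plan gives no figure to reproduce. The check is a count of items by section on tool 8 (before viewing) and tool 11 (after viewing).

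| Measure | Before (tool 8) | After (tool 11) | Paired |
|---|---|---|---|
| Attitude | 0 | 6 | no |
| Subjective norms | 0 | 6 | no |
| Perceived behavioural control | 0 | 5 | no |
| Donation intention | 0 | 3 | no |
| Intention of use | 3 | 0 | no |
| Acceptability | 3 | 3 | yes |
| Feasibility | 4 | 4 | yes |
| Cultural appropriateness | 3 | 3 | yes |
| Perceived usefulness | 3 | 3 | yes |
| Donor relatedness | 9 | 9 | yes |
| Docu-drama connectedness | 12 | 12 | yes |
| **Total** | **37** | **54** | |

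- After viewing only: 6 + 6 + 5 + 3 = 20 items in 4 constructs.
- Before viewing only: 3 items. The first reads "I would participate in a docu-drama viewing and discussion on blood donation in the next 6 months". Donation intention on tool 11 concerns giving blood, so it does not stand in for this measure.
- On both forms: 3 + 4 + 3 + 3 + 9 + 12 = 34 items in 6 scales.
- Totals agree: 37 = 34 + 3 and 54 = 34 + 20.

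A within-person change is the value after minus the value before. From these two forms it is available for 0 of 10 participants on each of the four planned-behaviour constructs and on intention of use. It is available for up to 10 of 10 on the six shared scales.

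**Could another form fill the gap?** Baseline A (tool 6, sections D to G) holds the same four constructs with 6, 6, 5 and 3 items.

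- Its instruction covers everyone at the study's baseline visit and is not restricted to the RCT, whereas Baseline B is restricted to RCT participants.
- Nothing assigns Baseline A to the test-run. Table 1 labels it as pre-randomization, and the randomization SOP places it directly before allocation. The test-run is not randomized and consists of one meeting.
- Study-wide wording does not settle the matter. The screening form is addressed to all volunteers for the study, yet it requires a smart phone and a WhatsApp account, which are not test-run criteria.
- Baseline A has no intention-of-use items and is not a post-viewing form, so that half of the gap remains even if it is used.

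**The case against.** The strongest counter-argument is that Baseline A already supplies the planned-behaviour pre-values. The RCT splits its baseline into a general form (A) and an intervention-specific form (B). The pre-viewing docu-drama form closely resembles B, without randomization and ease of use. On that view it was meant to follow A, and the silence of Table 1 and the SOP proves little because both are written for the RCT. This reading is possible. It makes the planned-behaviour half an ambiguity rather than a proven loss, but the documents do not state it, and it does nothing for intention of use.

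Other points stand in part:

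- The Secondary Outcomes list places attitude, norms, control and donation intention under WhatsApp and control only. For the docu-drama they come from the test-run promise and the Table 1 note. That limits their importance but does not remove the mismatch.
- Leaving intention of use off the post-viewing form agrees with the Table 1 row. It conflicts with the Table 1 note, with the 6–12 months text, and with the RCT text and Month 6 form.
- The group is 10 purposively selected, unrandomized donors, and the Data Analysis section specifies no paired docu-drama analysis.

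Two stronger readings are tempting. A reader might infer that the test-run can deliver no before-and-after comparison at all; the 34 shared items show otherwise, and they include all three survey measures of objective 3 that have scales (acceptability, feasibility and cultural appropriateness). A reader might also infer that knowledge and beliefs must be added to both forms. The secondary objectives mention them for the interventions in general, but the test-run promise does not name them and Table 1 gives them no row.

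**Conclusion.** The concern holds for five measures. As the two docu-drama forms stand, 20 planned-behaviour items have no value before viewing and 3 intention-of-use items have no value after viewing, against a promise made in three places. Six scales with 34 items are unaffected.

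The planned-behaviour part assumes that test-run participants do not complete Baseline A, which the documents leave unstated. The intention-of-use part holds on either reading.

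The consequence is confined to a descriptive test-run of 10 people. The primary outcome of the randomized pilot is not touched. The point is still worth acting on before the test-run, because the missing pre-values cannot be collected afterwards.

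**What to change.** 1. Add Baseline A sections D to G (20 items) to the pre-viewing form, or state in the test-run section that Baseline A is completed before viewing.
2. Add the 3 intention-of-use items to the post-viewing form.
3. Reconcile the Table 1 row for intention of use with the 6-month follow-up text and Month 6 section H, so that the RCT and the test-run follow one stated schedule.
4. State that paired changes in the test-run will be reported descriptively (n = 10).

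If the team does not want these measures at both times, the alternative is to narrow the three statements of what is surveyed.

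The cost is two form edits, a correction to Table 1 or the text, and a few minutes per participant: at most 20 × 10 = 200 further item responses before viewing and 3 × 10 = 30 after. No new visit or procedure is needed.

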- Intervention relatedness

Several measures are new or adapted: cultural appropriateness, acceptability, feasibility, perceived usefulness and perceived ease of use. These measures will be assessed for reliability.

The secondary outcomes will be determined through the use of questionnaires.

Sample Size Assumptions

Docu-drama design sample size

The planning of the docu-drama will involve participants who will take part in the drama design workshop discussion (n=20). In addition, we will recruit n=10 first-time donors to test-run and provide feedback on the newly designed docu-drama intervention.

WhatsApp intervention sample size

Key informant interviews (n=24) will help the team to identify how the WhatsApp platform will be used, and the WhatsApp intervention.

Pilot RCT sample size

The targeted sample size is 64 first time blood donors per treatment arm.

One of the primary objectives is to estimate the proportion of return blood donation for planning the randomized clinical trial in the UH3 phase. As the donor return rates are unknown given the Covid-19 pandemic, we focused on obtaining an acceptable precision of event rates for the sample size and power calculation for the UG3 phase. Figure 6 presents the sample size needed to achieve 80% confidence interval length equal to 0.15, 0.20, and 0.25 using the Exact (Clopper-Pearson) method, assuming the return rate ranging from 5% to 30% (Fleiss et al., 2003, Newcombe et al., 1998). A sample size of 59 produces a two-sided 80% confidence interval with a width equal to 0.149 when the sample proportion is 20%, which is the targeted donor return rate in the WhatsApp group. Considering 10% lost-to-follow-up, we would need a sample size of 64 for each treatment arm.

Alternatively, Figure 7 presents the minimum donor return rate in the WhatsApp group that can be significantly detected under various effective sample sizes and event rates in the control group. For example, if the donor return rate in the control group is 3%, an effective sample size of 59 in each group achieve 80% power to detect a minimum difference of 17.21% (i.e. the donor return rate in the WhatsApp group = 20.21%) when using the two-sided Fisher's exact test, with a 2-sided Type I error rate of 5%.

[figure not shown]

Figure 6: Sample size calculation based on precision

[figure not shown]

Figure 7: Alternative sample size calculation

Schedule of Assessments: Follow-Up

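### The enrolment target of 64 per arm is about two donors short of a 10% loss allowance on 59 evaluable; the effect on precision and power is small

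*Combined protocol and SAP*

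**What the plan says.** All of the relevant text is in the combined protocol and SAP, under Sample Size Assumptions, Pilot RCT sample size.

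- Enrolment target: "The targeted sample size is 64 first time blood donors per treatment arm".
- Main basis, which is precision: sample sizes are sought for an "80% confidence interval length equal to 0.15, 0.20, and 0.25 using the Exact (Clopper-Pearson) method". The chosen case is "A sample size of 59 produces a two-sided 80% confidence interval with a width equal to 0.149 when the sample proportion is 20" per cent, and 20% is the return rate targeted for the WhatsApp group.
- Loss allowance: "Considering 10% lost-to-follow-up, we would need a sample size of 64 for each treatment arm".
- Alternative basis, which is power: "if the donor return rate in the control group is 3%, an effective sample size of 59 in each group achieve 80% power". The effect in question is a WhatsApp rate of 20.21%, which lies 17.21 points above control, and the test is Fisher's exact, two-sided at 5%.

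Elsewhere, the Primary Objectives seek retention of at least 90%, which is the same 10% loss seen from the other side. The Quantitative Data Analysis section acknowledges that the pilot has low power to evaluate effectiveness.

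**The concern.** Both justifications rest on 59 evaluable donors per arm, and the enrolment figure is presented as 59 plus an allowance for 10% loss. If 64 does not leave 59 after 10% loss, then the enrolment target, the loss assumption and the quoted precision do not agree with one another.

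There is no slack to absorb the difference, because 59 is the smallest number that brings the width to 0.15 or less at a 20% return rate. A trial that only just met its 90% retention target would fall slightly below the number its precision statement relies on. The pilot is also meant to inform the UH3 trial, and the same inflation step, if reused there, would produce a shortfall of the same proportion.

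**Working it through.** **Inputs, all from the Pilot RCT sample size section.** Enrolled per arm 64; evaluable per arm 59; loss 10%; two-sided 80% Clopper-Pearson interval at a 20% return rate; two-sided Fisher's exact test at 5% with a 3% control rate and a 20.21% WhatsApp rate.

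**Step 1: reproduce the plan's own figures at n = 59.** With x = 0.20n, the Clopper-Pearson limits are the 10th percentile of Beta(x, n − x + 1) and the 90th percentile of Beta(x + 1, n − x). At n = 59 these are 0.1337 and 0.2827, a width of 0.1490. The smallest n with width at or below 0.15 is 59. Exact Fisher power, by enumerating all pairs of binomial counts at 3% and 20.21%, is 0.7998. Both stated figures reproduce.

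**Step 2: the loss allowance.**
- Required enrolment = evaluable / (1 − loss) = 59 / 0.90 = 65.6, so 66 per arm (132 in total, against 128 planned).
- Multiplying instead of dividing gives 59 × 1.10 = 64.9, which rounds up to 65. Only dropping the decimal gives 64.
- Evaluable from 64 at 10% loss = 64 × 0.90 = 57.6, that is 57 to 58.
- Largest loss at which 64 still leaves 59 = (64 − 59) / 64 = 5/64 = 7.8%.
- Check on 66: 66 × 0.90 = 59.4, so 59 is restored.

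**Step 3: the effect of having 57 or 58 evaluable instead of 59.**

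| Evaluable per arm | 80% width at 20% | Fisher power, 3% vs 20.21% | WhatsApp rate detectable with 80% power |
|---|---|---|---|
| 57 | 0.1518 | 0.780 | 20.70% |
| 58 | 0.1504 | 0.790 | 20.45% |
| 59 | 0.1490 | 0.7998 | 20.21% |

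The width grows by 0.0014 to 0.0028, power falls by 1 to 2 percentage points, and the detectable rate rises by 0.24 to 0.49 points.

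**Step 4: how much the width result depends on convention.** The plan's width uses a non-integer count (0.20 × 59 = 11.8 returns). Averaged over the binomial distribution at a true rate of 20%, the expected width is 0.1500 at n = 57 and 0.1486 at n = 58, at or just under 0.15. At n = 59 the width is 0.1456 with 11 returns, 0.1498 with 12 and 0.1537 with 13. One returning donor more or less moves the interval further than the inflation slip does.

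**The case against.** A reader might infer that the trial fails to deliver its stated precision and power. The documents do not support that, for four reasons.

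- **Precision is the design basis, and it is very nearly met.** The excess over 0.15 is at most 0.002 on the plan's own convention, and there is none in expected width.
- **The power sentence is conditional.** It gives 80% power for an effective 59 per group, not for 64 enrolled, and it remains true as written. It is offered as an alternative illustration in a pilot that acknowledges low power for effectiveness.
- **The comparison must hold the effect fixed.** At a WhatsApp rate of exactly 20%, power at 57 to 58 is 77.0 to 78.1%, but 59 evaluable gives only 79.1% there. Setting 77% against the stated 80% would mix a change of effect size with the loss.
- **The loss may not apply in full to the primary outcome.** Telephone reports of donor return are cross-checked with blood-centre records, and the anticipated analysis is intention-to-treat on all enrolled, with multiple imputation if necessary. If all 64 per arm were analysed, the width would be 0.1425 and power 0.844, both better than stated.

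It is also tempting to argue from the chance of ending with at least 59. With each donor 90% likely to complete, that is 0.37 for one arm of 64 and 0.14 for both arms. The plan sets no such test, and 66 per arm would reach only 0.66 and 0.44. An allowance for expected loss does not guarantee a minimum.

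The first three points stand and limit the finding to its small size. The fourth is possible but unsettled, because the documents do not say how participants who cannot be reached are counted. None of them makes 64 the result of a 10% allowance on 59, and the section itself treats loss as reducing the effective number.

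**Conclusion.** The loss-allowance sentence is wrong on its own inputs: 10% loss on 59 evaluable needs 66 per arm, and 64 allows 7.8%. At 10% loss, 57 to 58 donors per arm remain. The 80% interval width at a 20% return rate is then about 0.150 to 0.152 instead of 0.149, power for 3% against 20.21% is about 78 to 79% instead of 80%, and the minimum detectable WhatsApp rate is about 20.5 to 20.7% instead of 20.21%.

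These figures assume that loss removes donors from the primary-outcome denominator, as the sample-size section implies, and that it is equal in the two arms. The gap is two donors per arm. It is a minor correction to a stated figure and does not undermine the pilot's precision or power in any material way.

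**What to change.** Keep 64 per arm and replace the loss-allowance sentence with wording such as: *64 per arm allows about 7.8% loss to follow-up; at 10% loss, 57 to 58 donors per arm are evaluable, giving an 80% confidence interval width of about 0.15 at a 20% return rate and about 78 to 79% power for 3% versus 20.21%.* Add that 66 per arm is the enrolment that matches 59 evaluable at 10% loss.

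This costs one sentence and slightly less favourable stated figures. It changes neither the conduct nor the analysis of the pilot. If the sponsor prefers the stated figures to hold at 10% loss, the cost is two more donors per arm (132 instead of 128 in total).
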